#### Full structural model

For the post-intervention showing a significant intervention effect on children's psychosocial wellbeing, a parametric structural equation modelling approach, which is a statistical technique to test different pathways of the intervention effect on children's psychosocial

wellbeing (Structural Equation Modeling package in Stata version 18.0) will be used. We will estimate the total effect: the natural indirect effects (NIE), and natural direct effects (NDE) of BeThere on child psychosocial wellbeing for; (i) caregiver's scores (primary) and (ii) caregiver's scores (secondary) on Caregiver Distress, Caregiver Psychosocial Wellbeing and Harsh Parenting. The NDE represented the effect of BeThere on Child Psychosocial Wellbeing-parent report that was independent of Caregiver Psychological Distress, Caregiver Psychosocial Wellbeing, Caregiver Harsh Parenting. Caregiver Stress and Caregiver Stress Management. An NIE represented the proportion of BeThere that could be explained by its effect with changes in Caregiver Psychological Distress, Caregiver Psychosocial Wellbeing, Caregiver Harsh Parenting. Caregiver stress and Caregiver Stress management. To quantify the magnitude of mediation, the study will estimate the proportion of the effect mediated by Caregiver Psychological Distress, Caregiver Psychosocial Wellbeing, Caregiver Harsh Parenting., Caregiver stress and Caregiver Stress management (NIE/[NDE + NIE]). All analyses will be estimated using bootstrapping (500 replications) to recover the correct SEs for direct and indirect effects Results are presented as coefficients and 95 % confidence intervals from linear regression. Statistical significance was set a priori at p < 0.05 with no adjustment for multiplicity. Primary mediation analyses will be conducted using data from female caregivers, and secondary mediation analysis using combined data from male and female caregivers for each one of the multiple mediators.

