#### Trial design

#### Design

This study is a two-armed, parallel group randomized controlled trial, with an intent to treat design, a 1:1 allocation ratio, and a waitlist control comparison condition. The study will involve Dinka-speaking primary caregivers of children aged 3–14 and a subsample of their children aged 7–14 in five communities in Bor County, Jonglei State, South Sudan: Pariak, Ghoi, Taragok, Tibek, and Lenguet. Random allocation to intervention and control arms will be done at the family level to ensure caregivers from the same family do not participate in different arms of the study.

We will evaluate the effectiveness of BeThere—a nine-week preventative group psychosocial support intervention for primary caregivers of children aged 3-14-by measuring multiple parenting and psychosocial outcomes among participating caregivers compared to a waitlist control group of caregivers not participating in a parenting intervention. Quantitative data collection will be done by trained research assistants (RAs) using electronic tablets at four timepoints: baseline, midline, endline, and three-month follow up. Prior to the start of data collection, all research instruments will go through a process of translation, adaptation, cognitive interviewing, and pilot testing. The primary outcome of the study will be an overall score on parenting. Secondary outcomes will be child wellbeing (caregiver- and childreported), caregiver stress, distress, and wellbeing, as well as harsh parenting and parental warmth and responsiveness. Additionally, demographics data will be collected from caregivers and children. We will also record participant attendance to intervention sessions, along with facilitator competence to deliver the intervention and their fidelity in delivering the intervention as planned. Additional qualitative data will be gathered via focus group discussions and key informant interviews. The study will be conducted between January and July 2025.

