#### **Participants**

Participants will primarily be Dinka-speaking South Sudanese caregivers of children aged 3–14 years, with one index child per family. For families with more than one child in the stated age range, a random index child will be selected among families to be the focus in questionnaires. Thus, when caregivers are completing the parenting and child wellbeing questionnaires, they will do this only for the random index child. Similarly, the random index child will be the one to whom the child-reported questionnaire will be administered. The child-reported questionnaire will be administered to a sub-sample of index children aged 7–14. The total estimated sample size is 960 caregivers (equivalent of 480 families or more) and an estimated 400 index children aged 7–14. We will recruit caregivers from families with two caregivers, as well as from single-caregiver families (see section "Participant Recruitment" below). Thus, our sample of 960 caregivers consisting of: (i) dyads of caregivers for families with two caregivers; and (ii) individual caregivers from single-caregiver households. The total number of families therefore will be at least 480.

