#### Inclusion criteria

- At least 18 years of age
- Family with at least one child aged 3–14
- Willing to participate in the study and willing to commit to attending all nine sessions of BeThere if randomized to the intervention arm
- If both caregivers are present, they are both willing to participate
- Fluent in Dinka

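### The primary mediation model holds only the woman's mediators, but its direct effect is read as independent of caregiver mediators in general, although both caregivers are treated in two-caregiver families

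*Protocol*

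**What the plan says.** Three parts of the protocol bear on this.

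- **Who is treated.** Under Design: "Random allocation to intervention and control arms will be done at the family level". Under Participants, the sample holds "dyads of caregivers for families with two caregivers" as well as "individual caregivers from single-caregiver households". Under Inclusion criteria: "If both caregivers are present, they are both willing to participate". The Intervention section runs separate groups for women and for men. Each family has one index child.
- **Whose data enter the mediation.** Under Full structural model: "Primary mediation analyses will be conducted using data from female caregivers, and secondary mediation analysis using combined data from male and female caregivers". Earlier in the same section the two score sets carry the same label: "i) caregiver's scores (primary) and (ii) caregiver's scores (secondary". Only the closing sentence separates them by sex.
- **What the result is said to mean.** The same section states: "The NDE represented the effect of BeThere on Child Psychosocial Wellbeing-parent report that was independent of Caregiver Psychological Distress". It goes on to list caregiver wellbeing, harsh parenting, stress and stress management. The proportion mediated is NIE divided by the sum of NDE and NIE. Neither definition is limited to the female caregiver.

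This model is run only if the trial shows an effect on child wellbeing after the intervention.

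**The concern.** The quantity named and the model specified do not match. In a two-caregiver family the man also attends BeThere, and his distress, wellbeing and parenting can also affect the child. If only the woman's mediators are in the model, his route has no term of its own. An effect that runs entirely through caregivers could then be reported as partly direct, as if BeThere worked outside its own dual-pathway model.

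Confirming the mediation pathways is a named secondary objective, so the reading of this split matters. A spurious direct effect could also hide what fathers' participation adds, which bears on scale-up. The comparison of the arms on the parenting score is not affected.

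**Working it through.** The protocol attaches no figure to the split between NDE and NIE, so there is none to reproduce. Its sample-size numbers play no part here.

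**Model.** For a dyad family let X be the arm, and M_w and M_m one mediator for the woman and the man, with equal residual SDs and residual correlation r:

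- M_w = a_w·X + e_w
- M_m = a_m·X + e_m
- Y = b_w·M_w + b_m·M_m + e

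The true direct effect is set to zero, so true mediation through caregivers is 100%. The total effect is a_w·b_w + a_m·b_m.

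**What the women-only regression returns.** Given X and M_w, the expected M_m is a_m·X + r·(M_w − a_w·X). Substituting:

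- NIE = a_w·(b_w + r·b_m)
- NDE = b_m·(a_m − r·a_w)
- Proportion mediated = a_w·(b_w + r·b_m) / (a_w·b_w + a_m·b_m)

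The r·b_m term is the man's effect credited to the woman. The NDE is the rest of his effect. It is positive only while a_m exceeds r·a_w; it is zero at equality and negative beyond that. The planned adjustment for baseline measures and putative confounders does not remove this, because the man's mediators after randomization are themselves changed by treatment.

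**Inputs.** The protocol gives no path strengths by sex, no spouse correlation and no share of dyads, so all are assumed. Take a_w = b_w = 0.2, with every family a dyad.

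| Man's paths | r = 0 | r = 0.3 | r = 0.5 | r = 0.6 |
|---|---|---|---|---|
| Equal (0.2, 0.2): (1 + r)/2 | 50% | 65% | 75% | 80% |
| Both halved (0.1, 0.1): (0.04 + 0.02r)/0.05 | 80% | 92% | 100% | 104% |

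The second row shows the change of sign: NDE = 0.1·(0.1 − 0.2r) is 0.010, 0.004, 0 and −0.002.

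**Check by simulation.** With 400,000 families, a = 0.4 and b = 0.3 for both caregivers, the women-only model gave 0.50, 0.65 and 0.82 at r = 0, 0.3 and 0.6. Entering both caregivers' mediators gave an NDE of about 0 and a proportion of about 1.0.

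**Single-caregiver families.** As a rough approximation, scale the man's b path by the dyad share D. For equal paths the proportion is (1 + rD)/(1 + D). At r = 0, 0.3 and 0.6 this gives 57%, 70% and 83% with D = 0.75, and 67%, 77% and 87% with D = 0.5.

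**Averaging the two caregivers.** The slope on the family mean is b_w + b_m, and the arm effect on that mean is (a_w + a_m)/2. In the halved case this gives 0.15 × 0.3 / 0.05 = 90% at every r. That is closer to the truth than women-only at r = 0 (80%), but further from it at r = 0.3 (92%) and r = 0.5 (100%).

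**The case against.** An NDE is always relative to the mediators in the model, and the same section says whose data those are. Women-only is also a defensible primary choice: it gives about one record per family, and the protocol needs special strategies to recruit men. That stands, and the women-only model can stay. What it does not justify is an unrestricted reading of the NDE.

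The sizes rest on assumed inputs, and 50% is an extreme case. The structural model's outcome is parent-reported and outcome measures come from every caregiver, so a women-only model would presumably use the woman's own report. The man's path to that report may be weaker, and shared reporting may strengthen hers. Neither is modelled above. This limits the size, not the mismatch.

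A reader might infer three stronger points that the documents do not support.

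- *That the combined secondary analysis stacks caregivers as separate rows and so cannot help.* The protocol says only that male and female data are combined for each mediator, which also fits a family-level combination. If rows were stacked, the simulated proportions would be about the same as women-only (0.51, 0.66 and 0.82), but that is one reading.
- *That mediation is always understated.* The halved case reaches 100% and then 104%.
- *That the proportion mediated is the headline of the mediation objective.* That objective speaks of power for sequential mediation and of confirming pathways. The proportion appears only under Full structural model.

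**Conclusion.** The point holds as a mismatch between the women-only primary model and the meaning given to its NDE and proportion mediated. In two-caregiver families the effect carried by the man is split between the NDE and, through spouse correlation, the woman's NIE. The bias in the proportion mediated through caregivers is usually downward, but its sign depends on whether a_m exceeds r·a_w.

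With true mediation of 100%, all families dyads and r from 0 to 0.5, the illustrative results are 50% to 75% for equal paths and 80% to 100% when both of the man's links are half as strong. The bias is smaller with more single-caregiver families, whose share is not given. All these sizes rest on assumed path strengths, correlation and dyad share, in a linear model with one mediator per caregiver and one shared child outcome. The documents do not show that the women-only model must be replaced.

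**What to change.** 1. Keep the women-only model if wanted, but define its NDE as the effect not through the female caregiver's mediators, and its proportion mediated as the share through them. Do not read that NDE as an effect that bypasses caregivers.
2. Prespecify a family-level analysis in two-caregiver families, with one record per family and each mediator entered separately for the woman and the man, not averaged.
3. State that the combined secondary analysis takes this form.

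The mediators are already collected from all participating caregivers, so the cost is wording and one added model. The downside is that the dyad model has more parameters and covers two-caregiver families only.

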#### **Statistics**

#### Power and sample size

To gain a general appreciation for the required sample size to detect an indirect effect through the primary mediators (Caregiver Distress, Wellbeing, and Harsh Parenting), we used the sample size estimator for joint significance indirect effects developed by Vittinghoff and Neilands (2015). With a two-sided alpha of 0.05, for an intervention-mediator error term correlation coefficient of 0.2, a standard deviation of the mediator of 0.2, and a standard deviation of the random error term of 0.5, a sample of 425 caregivers per group would be sufficient to detect a mean difference of 0.4 (Vittinghoff & Neilands, 2015). All parameter estimates are based on our previous work. Sample size estimators for multiple mediator models are currently unavailable (VanderWeele, 2016); however, O'Rourke and Mackinnon (2015) provide evidence that multiple mediator models have more power than single mediator models. Thus, we expect this study to have sufficient power for multiple mediator models. With a 10% attrition we expect to have 468 families per group with 234 children, totaling 936 caregivers and 468 children. With a total of 40 intervention groups, the final sample size is 960 caregivers (equivalent of 480 families or more) and 400 index children.

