We will investigate the mediation process of different aspects of caregiver wellbeing and parenting and, through that, examine how these factors affect child wellbeing, helping us understand how best to achieve downstream effects on child wellbeing through psychological interventions. Some of the pathways of interest are illustrated in Figure 4.

[figure not shown]

[figure not shown]
Figure 6 Primary mediation pathways

If the efficacy analysis shows significant between-group differences in the mediators (caregiver stress, caregiver distress, caregiver psychosocial wellbeing, and parenting), then we will use parametric regression models to:

[figure not shown]
- Test for mediation of the intervention on child wellbeing through caregiver stress
- Test for mediation of the intervention on child wellbeing through caregiver distress
- Test for mediation of the intervention on child wellbeing through caregiver psychosocial wellbeing
- Test for mediation of the intervention on child wellbeing through parenting

Since all the measures are continuous, the indirect effects will be calculated by multiplying relevant pathways and bootstrapping will be used to produce valid standard errors for the indirect effects. All analyses will adjust for baseline measures of the mediators (caregiver stress, caregiver distress, caregiver psychosocial wellbeing, and parenting), the outcome (child wellbeing) and putative measured confounders (e.g., socioeconomic status).

Furthermore, these factors will also be analyzed through three sequential mediation models (Figure 5), to assess how the downstream effect of BeThere on child wellbeing is mediated first through (1) caregiver wellbeing, (2) caregiver distress, and (3) caregiver stress, and then through parenting.

Finally, we will also measure the effect of BeThere on caregiver wellbeing, stress, and distress, as mediated through cohesion among the intervention group (Figure 6).

We will assess for the effect of the BeThere intervention on each one of the multiple continuous mediators with the use of linear regression models. We chose an a priori *p*-value of lower than 0.15 to select the appropriate mediators to include in our final mediation analysis (VanderWeele & Vansteelandt, 2014). Multiple mediators require independence with each other. Therefore, we will test independence by examining partial correlations between our mediators after accounting for treatment allocation.

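### Trial sized for a joint-significance test of mediation, while the analysis text bootstraps only standard errors; on its natural reading this is a weaker, conservative test at the female-only sample size

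*Protocol*

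**What the plan says.** Protocol, Power and sample size: "we used the sample size estimator for joint significance indirect effects". The inputs are a two-sided alpha of 0.05, a correlation of 0.2, a mediator SD of 0.2 and an error SD of 0.5, from which "a sample of 425 caregivers per group would be sufficient to detect a mean difference of 0.4". No target power is stated.

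Protocol, Analyses: indirect effects are products of the relevant paths, and "bootstrapping will be used to produce valid standard errors for the indirect effects". Three sequential models (a caregiver variable, then parenting, then child wellbeing) are added.

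Protocol, Full structural model: "All analyses will be estimated using bootstrapping (500 replications) to recover the correct SEs for direct and indirect effects". Results are given as coefficients with 95% confidence intervals, described as coming from linear regression, and significance is p < 0.05. Women's data form the primary mediation analysis; the combined male and female data form the secondary one.

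Neither analysis section names joint significance, a normal-based interval, a percentile interval or a bias-corrected interval.

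**The concern.** Joint significance declares mediation when every path is significant on its own. An estimate divided by its bootstrap standard error is a different test. It treats the product of two or three coefficients as normal, although that product is skewed. With the first-order standard error the two-path statistic is z_a·z_b/√(z_a² + z_b²), which is always smaller than either path's own z. Two paths each at z = 2.7 give 2.7/√2 = 1.91, and three paths each at 3.3 give 3.3/√3 = 1.91. Neither reaches 1.96, although every path is clearly significant.

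Objective 3 says the study has full power to confirm the sequential mediation pathways. If the test applied is weaker than the test used for sizing, real indirect effects are missed more often than the sizing implies, and a negative mediation result is harder to interpret.

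**Working it through.** **Inputs from Power and sample size.** Correlation ρ = 0.2 ("for an intervention-mediator error term correlation coefficient of 0.2"), taken as the intervention-mediator correlation; "a standard deviation of the mediator of 0.2"; "a standard deviation of the random error term of 0.5"; alpha 0.05 two-sided. The 0.4 is read as the mediator-outcome coefficient b. Read instead as a difference of two means with SD 0.5, it would need only 25–33 per group, which does not fit 425.

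**The plan's own figure.** For the mediator-outcome path, n = (1.96 + z_power)²·SD_e² / (b²·SD_m²·(1 − ρ²)). At an assumed 90% power this is (1.96 + 1.2816)² × 0.25 / (0.16 × 0.04 × 0.96) = 427.6. That is close to 425, but as a total and for this path alone. Because the target power is not stated, 425 per group cannot be reproduced outright. Both totals, about 425–432 and 850, are therefore carried below.

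**Size of the primary mediation set (assumed).** One woman in each of 480 families with 10% attrition gives 480 × 0.9 = 432. More than 480 families, for instance with more single mothers, would raise this.

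**Single mediator, N = 432.**
- z_a = 0.2 × √432 / √0.96 = 4.243, power 98.9%.
- z_b = 0.4 × 0.2 × √0.96 × √432 / 0.5 = 3.258, power 90.3%.
- Joint significance: 0.989 × 0.903 = 89.3%.
- Symmetric z-test of the product, by Monte Carlo: 81.1% (first-order SE) or 79.0% (exact-variance SE).
- Simulated datasets with 500 resamples each (1,500 datasets per run, two separate runs): joint 87.3% and 88.8%; bootstrap-SE z-test 77.9% and 78.6%; percentile interval 87.7% and 88.9%.

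**Single mediator, N = 850.** Joint 99.5%, z-test 99.2–99.3%.

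**Sequential chain, N = 432.** The outer paths are as above. The middle correlation is assumed, because the protocol gives none.

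| Middle correlation | Joint | z-test (first-order / exact-variance SE) | Loss, points |
|---|---|---|---|
| 0.10 | 49.2% | 14.9% / 11.1% | 34–38 |
| 0.15 | 78.9% | 39.8% / 32.8% | 39–46 |
| 0.20 | 88.3% | 61.8% / 55.0% | 26–33 |
| 0.30 | 89.3% | 76.2% / 72.3% | 13–17 |
| 0.50 | 89.2% | 79.9% / 77.4% | 9–12 |

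At N = 425 the largest loss is 47 points (correlation 0.15). Simulated datasets at N = 424 with 500 resamples give losses of 44, 35, 22 and 17 points at correlations 0.15, 0.2, 0.3 and 0.5. The percentile interval stays within about 1 point of joint significance in each.

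**Sequential chain, N = 850.** The loss is 15–19 points at correlation 0.1, about 3–5 at 0.15, about 1 at 0.2, and under 1 from 0.3 upward.

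**False positives.** With no effect on the mediator and a real mediator-outcome path (z_b = 3.26), joint significance rejects in 4.5% of trials and the z-test in 1.2–1.4%.

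None of these figures models family clustering, covariate adjustment or the conditions that must be met before the mediation analyses are run.

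**The case against.** The protocol never says that the test is a symmetric z-test. It says standard errors, 95% intervals and p < 0.05, and an analysis plan could still name a percentile interval. The sample-size section also offers its calculation only as a general guide, not as a commitment to a test. And the error is on the safe side: a conservative test does not create false mediation claims.

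Part of this stands. The z-test is an inference and should be described as one. But the text is not merely silent: in two places it says that the bootstrap is there to supply standard errors, and it attaches p-values and regression-type intervals to the results. If percentile intervals were intended, the wording should still change, and 500 replications leave only about 12 draws in each 2.5% tail.

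A reader might infer that the chains lose some 40 points of power, or that single mediators lose 10 points at the stated sample size. The documents support neither. The first needs a weak middle path (about 0.15) that they do not state, together with the smaller N. The second holds at about 432 in total; at 425 per group the loss is under 1 point. Nor is roughly 89% the power the trial would achieve, since clustering and the gating conditions are left out.

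**Conclusion.** The concern holds in conditional form. The test used for sizing and the inference described for the indirect effects do not match. On the natural reading of the analysis text, the latter is conservative, with a false-positive rate of about 1% in the null case examined, and less powerful.

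At an assumed 432 women, single-mediator power falls from about 88–89% to about 78–81%. The chains lose roughly 9 to 47 points over assumed middle correlations of 0.1 to 0.5. In the combined-sex secondary analysis, at about 850, the loss is negligible for a single mediator and small for chains unless the middle path is weak.

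The conclusion rests on the z-test reading, on 0.4 being the mediator-outcome coefficient, and on one woman per family with 10% attrition. It concerns secondary objective 3 only; the primary parenting comparison by linear mixed model is untouched.

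**What to change.** In Analyses and in Full structural model, replace the statements that the bootstrap serves to obtain standard errors. State instead that two-path and three-path indirect effects are judged by the percentile bootstrap 95% confidence interval, with for example 5,000 resamples, or by the joint-significance test used for sizing. Name the chosen one as the criterion for concluding mediation, in place of intervals described as coming from linear regression.

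This needs no further participants or data. The cost is a wording change and some computing time.

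### The sample-size figure for mediation, 425 per group, is reached only by pooling women and men, but the primary mediation analysis is restricted to women

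*Protocol*

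**What the plan says.** Protocol, Power and sample size, bases the trial size on an indirect effect through caregiver distress, wellbeing and harsh parenting. It states that "a sample of 425 caregivers per group would be sufficient to detect a mean difference of 0.4". The calculation does not mention sex and prints no power. The attrition step reads: "With a 10% attrition we expect to have 468 families per group with 234 children, totaling 936 caregivers and 468 children". The final size is 960 caregivers, equated with 480 families or more.

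Participants says the 960 are made up of "dyads of caregivers for families with two caregivers" plus individual caregivers from single-caregiver households, with one index child per family. Randomization allocates whole families and gives 480 caregivers per arm, women and men together.

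Full structural model then sets the analysis population: "Primary mediation analyses will be conducted using data from female caregivers, and secondary mediation analysis using combined data from male and female caregivers".

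The Study Synopsis and the secondary objectives describe the trial as fully powered for mediation. The Protocol gives no expected number of women and no sample size for a women-only analysis.

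**The concern.** The size is computed in one population, caregivers of both sexes, and the primary mediation analysis is run in another, women only. Nothing in the Protocol connects the two. If 425 per group is the right figure, the primary mediation analysis will not have it under any plausible family mix. If it is not, the sample-size statement is wrong. One of the two passages has to change.

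The attrition sentence adds to the confusion. Taken literally, 468 families per group would supply about 468 women per group, and the women-only analysis would look amply sized. The totals in the same sentence rule that out.

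At stake is the secondary objective on mediation. A null result in women cannot be interpreted unless the plan says what effect that number of women could detect. The primary comparison on parenting uses all caregivers and is not affected.

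**Working it through.** **1. The plan's own inflation.** 425 × 1.10 = 467.5, rounded to 468 per group, and 2 × 468 = 936 caregivers. This reproduces the printed total. Dividing by 0.90 would give 473 per group (946 in total); the final 960 covers either.

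**2. Units in the attrition sentence.** 936 caregivers over two arms is 468 caregivers per group. With one index child per family, 234 children per group means 234 families per group, or two caregivers per family. 468 families per group would mean 936 families in all, which the printed 936 caregivers and 468 children do not allow.

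**3. Pooled sample after attrition.** 480 × 0.90 = 432 per arm, just above 425.

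**4. Women after attrition.** The Protocol does not state the number of women, so this step rests on assumptions: one woman per two-caregiver family, and 10% attrition in women as in men.

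- All families are couples: 480 families ÷ 2 arms = 240 women per arm; 240 × 0.90 = 216; 216/425 = 51%.
- With *d* two-caregiver families there are 960 − 2*d* single caregivers. If all of these are women, women per arm = (960 − *d*)/2:

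| Two-caregiver families | Women per arm randomised | After 10% attrition |
|---|---|---|
| 400 | 280 | 252 |
| 300 | 330 | 297 |
| 200 | 380 | 342 |

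- These are upper limits for each *d*; every single male caregiver lowers them.
- To keep 425: (960 − *d*)/2 × 0.90 ≥ 425 requires *d* ≤ 15.6, so at most 15 two-caregiver families in the trial. Put as a share, 425/432 = 98.4% of caregivers would have to be women. The Recruitment section plans specific measures to recruit men.

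**5. What the printed inputs yield.** The inputs are "With a two-sided alpha of 0.05"; "for an intervention-mediator error term correlation coefficient of 0.2"; "a standard deviation of the mediator of 0.2"; an error standard deviation of 0.5; and an effect of 0.4, read here as the mediator-outcome coefficient.

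- Standard formula for the mediator-outcome path: N = (z₁ + z₂)² × σₑ² / (b² × σₘ² × (1 − ρ²)), where N is the total sample.
- At 90% power: (1.96 + 1.282)² × 0.25 / (0.16 × 0.04 × 0.96) = about 428 in total. At 80% power: about 319.
- The 90% result agrees with 425 to within 1%, but as a total. The corresponding totals are 365 at 85% power and 529 at 95%; none of these is near 850, which 425 per group would need.

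**6. Power under those inputs.**

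- Total of 432 women (216 per arm): mediator-outcome path Φ(√(432 × 0.006144/0.25) − 1.96) = Φ(1.30) = 0.903; intervention-mediator path Φ(√(432 × 0.04/0.96) − 1.96) = Φ(2.28) = 0.989; joint 0.903 × 0.989 = 0.893.
- Total of 850 (425 per group): joint power about 99.5%.

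**The case against.** The strongest reply is that no loss of power has been shown, and that stands. A reader might infer that halving the sample leaves the primary mediation analysis badly underpowered. If 425 per group were assumed to give 80% or 90% power, scaling to 216 would give about 51% or 64%. The Protocol does not support this: it prints no power, and its own inputs give 425 per group a joint power above 99%, and 432 women in total about 89%. The inputs suggest that a total was labelled as a per-group figure.

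Three further points are fair:

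- The section calls 425 sufficient, not required, and offers the calculation as a general guide. Missing a sufficient number does not by itself mean too little power.
- 216 is not the sponsor's number. It is the all-couples case, and the Protocol allows more than 480 families. It should not be written into the plan as the expected count.
- The women-only sentence stands under Full structural model. The sequential mediation models, to which the objective of full power refers, are described under Analyses without restriction by sex. Whether the sentence covers them too is unclear.

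A reader might also take the switch from caregivers to families as an attempt to mask the shortfall. The text shows only a slip of units.

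None of this removes the inconsistency. If 425 is per group, the primary analysis does not get it; if it is a total, the text says otherwise. This is not a detail left to a statistical analysis plan, because the Protocol itself fixes both the size and the conflicting population.

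**Conclusion.** The point holds as an inconsistency within the Protocol. The figure of 425 per group is met only by the combined analysis, which is secondary. The primary, women-only analysis would have 216 per arm after attrition if all families are couples with one woman each. It would have 252 to 342 with 400 down to 200 two-caregiver families if every single caregiver is a woman. It falls short of 425 unless about 98% of caregivers are women. Separately, 468 families per group is wrong on the sentence's own totals.

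Underpowering is not established. It depends on an unstated power and on whether 425 is per group or total. The calculation that points to a total rests on reading the 0.4 as the mediator-outcome coefficient in the standard formula.

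**What to change.** In Power and sample size:

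- State the power and whether 425 is per group or total.
- Restate the calculation for women. Give the expected number of women per group, randomised and analysed, as a range tied to the share of two-caregiver families, and the indirect effect detectable at that number.
- Correct 468 families per group to 468 caregivers per group (234 families at two caregivers each).

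In Full structural model and Analyses, say whether the restriction to women also applies to the sequential mediation models.

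In the Study Synopsis and Objectives, align the statements of full power for mediation with the restated result.

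The cost is rewording and one recalculation, with no extra recruitment. If 425 per group is confirmed as the intended figure, the stated power for the primary mediation analysis will become less favourable. If it was a total, the claim may largely survive.
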